Risk / Benefit Assessment	This study will provide valuable insight into optimising patient care and reducing complications, given the significant burden of esophageal cancer and its treatment. Reducing DGCE with a simple, safe and often used measure such as balloon dilatation of the pylorus would drastically reduce the morbidity of esophagectomy. Since the balloon dilatation would be done at the beginning of the surgery, risks of the intervention are minimal. Measures such as robust safety protocols, informed consent and privacy measures will be used to protect participants throughout the trial to balance the generally occurring risks of the study and to protect all participants from potential harming.
Objective(s)	Our aim is to investigate if intraoperative endoscopic balloon dilatation reduces the incidence of DGCE in the early postoperative course (until three months postoperatively). Furthermore, we investigate if mechanical balloon dilatation reduces the risk for postoperative complications, hospital stay, time to first bowel movement, and improves quality of life (QoL) after esophagectomy.
Endpoint(s)	Primary endpoint: - Incidence of early DGCE in postoperative course (after 5 and 10 days, measured using radiological and clinical parameters) Secondary: - Incidence of late DGCE (after more than 14 days postoperatively) - Rates of anastomotic leak - Complication rates using Clavien Dindo classification - Hospital stays in days - Time to first bowel movement - Time to first solid food intake - Postoperative Quality of life (assessed with the EORTC QLQ-OES18 questionnaire)
Study Design	This study is a single center, double blinded, superiority randomized controlled trial.
Inclusion- / Exclusion Criteria	Inclusion criteria: - Age >18 years - Histologically confirmed esophageal cancer

	
 - Planned surgical resection in curative intent as a minimally invasive Ivor Lewis procedure - Provided informed consent 
Exclusion criteria:
 
 - Prior esophageal or gastric resection - Non-curative intent of surgery - ASA Score V - Patients lacking capacity to provide informed consent

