Statistical Considerations:	The statistical analysis is performed according to an intention to treat analysis. Chi-square tests is used for categorical variables and t-tests or Mann-Whitney U tests for continuous variables. Multivariable logistic regression will be used to adjust for potential confounders.
Data privacy	Data are collected from patient's electronic data system (Phoenix®/Meona) at St. Claraspital and the University hospital of Basel. Data is then encoded (from 1 to number of patients) and stored onto a Redcap Database with only personalized access.
Ethical consideration	The aim of this randomized controlled trial (RCT) is to demonstrate that intraoperative endoscopic balloon dilation reduces DGCE, thereby improving quality of life, reducing

	morbidity of the patients, shortening hospital stay and lowering treatment costs in patients with esophageal cancer. Endoscopic balloon dilatation is an established, safe and frequently used method. The risk for complications after balloon dilatation is low.
GCP Statement	This study will be conducted in compliance with the protocol, the current version of the Declaration of Helsinki, the ICH-GCP, the HRA as well as other locally relevant legal and regulatory requirements.

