Men are more frequently affected by esophageal cancer than women. The risk of developing esophageal cancer increases with age. Radical surgical removal of esophageal carcinomas is the only curative therapy available today, especially in EAC. However, the operation is associated with high postoperative morbidity and a high complication rate and a 90-day mortality rate of around 4% (17). Thoracoabdominal resection with creation of a gastric tube or, if possible, transhiatal resection are currently the standard operations for esophageal carcinomas (16). Some of the most important postoperative complications after esophagectomy are anastomotic leak, pulmonary complications such as pneumonia and chylothorax, as well as delayed gastric conduit emptying (DGCE) and dysphagia. DGCE refers to impaired or slowed passage of gastric contents through the conduit, leading to prolonged gastric retention after esophagectomy. It causes symptoms such as nausea, vomiting, regurgitation and inability to tolerate oral intake. DGCE is described in up to 40 percent of patients after esophagectomy and therefore presents a great burden in these patients (8,9). The DGCE can put mental and physical stress on these patients. Also, DGCE may increase the risk of anastomotic leaks through the increased pull on the new esophago-gastric anastomosis. Due to the prolonged recovery, the time until discharge from the hospital and start of rehabilitation is significantly delayed as a result of DGCE. The DGCE also results in higher costs which place an additional burden on the healthcare system.

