3.2 Primary and secondary endpoints

The Primary outcome is defined as incidence of early DGCE. Early DGCE is defined as presence of a nasogastric tube with an output of >500ml on day 5 or later and/or >100 % increased gastric tube width on radiological chest X-Ray on

day 5 or later (in comparison with baseline X-Ray upon admission on the ICU). DGCE will be diagnosed using both of these mentioned radiological and clinical tools on day 5 and 10 (10).

As secondary endpoints we define the incidence of late DGCE measured using the symptom orientated DGCE questionnaire and a radiological passage examination after 3 months. Furthermore, we want to investigate potential differences between the two groups concerning the rate of anastomotic leaks, postoperative complications such as pneumonia, duration until first bowel movement after surgery, duration until first intake of solid food, presence of vomiting during the postoperative course and length of hospital stay. In addition, we will analyze the quality of life via symptom orientated questionnaires after 3 months using the EORTC QLQ-OES18 questionnaire.

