
4.4 Withdrawal and discontinuation

Patients who withdraw consent and also withdraw of permission to collect further clinical information will be included in the intention-to-treat analysis, but no study-specific follow-up will be performed. All participants who withdraw from the study are no longer involved in the study and no further data collection is performed. If a participant refuses to participate in the study after the hospitalization the participant will be included in the intention to treat analyses. If a patient withdraws the informed consent before the surgery is performed the participant will be excluded from the study.

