5 STATISTICS AND METHODOLOGY

5.1. Statistical analysis plan and sample size calculation

The aim of this power analysis was to calculate the minimum required sample size for our randomized controlled trial (RCT) investigating the effect of intraoperative endoscopic pyloric dilatation on the incidence of early delayed gastric conduit emptying (DGCE) within the first 14 days after esophagectomy.

The sample size calculation for this study was based on findings from Boshier et al. (18), which demonstrated a reduction in the incidence of DGCE from 48% to 22% following intraoperative pyloric stretching procedures. To achieve a statistical power of 80% ($1 - \beta = 0.80$) while maintaining a Type I error rate of 0.05 ($\alpha = 0.05$), a power analysis for comparing two independent proportions was performed. The absolute difference in proportions (Δ) was set at 26 (0.48

- 0.22). Using these parameters, the required sample size was calculated to be 52 patients per group, resulting in a total of 104 patients for the study. This ensures sufficient power to detect a statistically significant difference in DGCE incidence between the two treatment groups.

To account for potential dropouts or loss to follow-up, an estimated attrition rate of 10% was considered. Consequently, the final target enrolment is increased to 58 patients per group, leading to a total of 116 patients. This adjustment maintains adequate statistical power even if a subset of participants does not complete the study.

The statistical analysis will be conducted according to the intention-to-treat (ITT) principle. Categorical variables will be analyzed using Chi-square or Fisher's exact test, while continuous variables will be evaluated using either independent t-tests or Mann-Whitney U tests, depending on the distribution. Multivariable logistic regression analysis will be used to adjust for relevant covariates and potential confounding factors.

All statistical analyses will be performed in collaboration with an experienced statistician from our research group using validated software such as SPSS or R. A significance level of $p < 0.05$ will be considered statistically significant for all tests.

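### By default, time to solid food, time to bowel movement and hospital stay go to a t-test or Mann-Whitney U test that has no place for death or for not reaching the event

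*Protocol*

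**What the plan says.** The synopsis lists, among the secondary endpoints, "Hospital stays in days - Time to first bowel movement - Time to first solid food intake". Section 3.2 repeats them, for example as "duration until first bowel movement after surgery, duration until first intake of solid food", together with length of hospital stay. Neither place says what value a patient receives who dies, or who leaves hospital, before the event.

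Section 5.1 assigns methods by type of variable. Categorical variables get chi-square or Fisher's exact tests; for the rest, "continuous variables will be evaluated using either independent t-tests or Mann-Whitney U tests, depending on the distribution". The synopsis has the same pair: "t-tests or Mann-Whitney U tests for continuous variables". The only other method is regression: "Multivariable logistic regression analysis will be used to adjust for relevant covariates and potential confounding factors". No survival or competing-risk method appears anywhere in the protocol.

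Section 5.1 also commits the trial to intention to treat: "The statistical analysis will be conducted according to the intention-to-treat (ITT) principle". Section 4.4 keeps patients who withdraw after surgery in that analysis, yet states: "All participants who withdraw from the study are no longer involved in the study and no further data collection is performed".

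**The concern.** A t-test needs a finite number from every patient. A Mann-Whitney U test needs at least a rank. The protocol's own background shows that some patients will have neither unless a rule supplies one.

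- **Death.** Section 2 cites a "90-day mortality rate of around 4" per cent.
- **Not reaching the event.** Section 2 counts failure to tolerate feeding by mouth among the symptoms of DGCE. The condition under study can therefore prevent the solid-food event, and missing times would cluster in DGCE patients. If the trial hypothesis is true, more of these are controls, and an analysis of observed values is pulled toward no difference.
- **Hospital stay.** A patient who dies on day 6 has six recorded hospital days. A mean or rank comparison reads that as fast recovery.

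The synopsis counts shorter hospital stay and earlier bowel movement among the trial's aims, so these comparisons will be read as evidence of faster recovery. Losing patients for reasons tied to outcome and arm would sit badly with the intention-to-treat commitment. Letting the observed distribution choose the test adds a data-driven step that can be avoided.

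**Working it through.** **1. The plan's own figure.** The protocol gives no figure for the three durations. Its primary-endpoint sample size reproduces. With 0.48 v 0.22, two-sided alpha 0.05, power 0.80, pooled variance and mean proportion 0.35:

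n = [1.96 × √(2 × 0.35 × 0.65) + 0.842 × √(0.48 × 0.52 + 0.22 × 0.78)]² / 0.26² = 51.6, so 52 per group. Then 52 / 0.9 = 57.8, so 58 per group and 116 in total. Nothing below alters this.

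**2. Expected deaths.** At the cited 4% by 90 days, 116 × 0.04 = 4.6 deaths, about 2.3 per arm. The chance of at least one is 1 − 0.96^116 = 0.99. For an assumed 2% to 6%, the expected number is 2.3 to 7.0. The protocol does not say how many would fall in hospital or before the event.

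**3. Solid food: missing values.** Let f be the share of DGCE patients with no solid food by discharge (assumed). Take every death as preceding solid food, which is an upper bound. The share without a value is 0.04 + 0.96 × (DGCE rate) × f.

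- f = 20%: control 0.04 + 0.96 × 0.48 × 0.20 = 13%; dilatation 0.04 + 0.96 × 0.22 × 0.20 = 8%.
- f = 40%: control 22%; dilatation 12%.

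**4. Solid food: power.** Simulation with 58 per arm, DGCE 48% v 22% and 4% deaths. The event times are assumptions with no source in the protocol: log-normal, median 6 days, log-SD 0.35, lengthened 1.35- or 1.65-fold by DGCE. Mann-Whitney U power at two-sided 0.05:

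| f | 1.35-fold: dropped v ranked last | 1.65-fold: dropped v ranked last |
|---|---|---|
| 0% | 0.20 v 0.18 | 0.38 v 0.33 |
| 5% | 0.19 v 0.20 | 0.35 v 0.36 |
| 10% | 0.16 v 0.19 | 0.35 v 0.36 |
| 20% | 0.16 v 0.24 | 0.31 v 0.39 |
| 40% | 0.13 v 0.33 | 0.22 v 0.45 |

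At 0%, ranking last costs 2 to 5 points. At 5-10% it gains 1 to 3, which is near simulation error. At 20% it gains 8, and at 40% it gains 20 to 23.

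**5. Hospital stay: false-positive rate.** Null simulation, all inputs assumed: 58 per arm, log-normal stay with median 14 days and log-SD 0.5, deaths uniform over days 1 to 14, no effect on survivors' stay. Chance of a significant result favouring dilatation (nominal 2.5%):

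| Deaths, control v dilatation | Death as short stay | Deaths dropped | Deaths ranked last |
|---|---|---|---|
| 4% v 4% | 2.7% | 2.9% | 2.6% |
| 2% v 6% | 3.6% | 2.2% | 0.8% |
| 4% v 10% | 6.1% | 2.8% | 0.7% |

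With equal mortality the coding hardly matters. With 4% v 10%, the short-stay coding makes the median stay in the dilatation arm look about half a day shorter.

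**6. Bowel movement.** No figure was computed. Nearly all survivors should reach this event early (assumption), so few values would be missing.

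**The case against.** The sentence in section 5.1 is generic and names none of the three endpoints. A reader might infer that the protocol drops patients who never eat solid food, counts an in-hospital death as a short stay, and so breaches its own intention-to-treat rule. The text supports none of these. They are what usually happens when the named tests are run on observed values, not stated rules. This part of the objection stands.

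It can also be said that the Mann-Whitney U test is already named, and that a coding rule for death or non-attainment is ordinary material for a statistical analysis plan. This stands in part: silence on the coding alone would not be a finding. But section 5.1 does fix a family of tests for these durations, and one of the two, the t-test, cannot accommodate a patient without a finite time.

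The power loss rests on an unsourced share of DGCE patients who leave without solid food. This stands fully. With deaths alone, ranking last is slightly the weaker analysis. For hospital stay, distortion needs unequal mortality, and the protocol gives no reason to expect it. For solid food the bias runs toward no effect, which is conservative in a superiority trial.

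Finally, choosing between the two tests by distribution is conventional, and no harm from it was quantified here.

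**Conclusion.** The point holds as a minor one on secondary endpoints. By elimination, section 5.1 sends the three durations to tests that, on observed values, have no place for death or non-attainment, although the protocol's background leads one to expect both.

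- **Solid food.** This is where it could matter. If 20-40% of DGCE patients had no solid food by discharge, dropping them would cost about 8 to 23 points of power under the assumed event times. At 0-10% it costs little or nothing.
- **Hospital stay.** Negligible with equal mortality; a false-favourable rate of 3.6% to 6.1% in the two unequal-mortality cases.
- **Bowel movement.** Likely small.

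It would go too far to say that the plan excludes these patients or abandons intention to treat: it states no such rule. It would also go too far to quote the power loss as a property of this trial, because the event times and the non-attainment share are assumptions. The primary endpoint, its analysis and the 58 per group are untouched.

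**What to change.** In section 5.1, name one analysis for these three endpoints in place of the clause that lets the distribution decide.

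- **Simplest:** a Mann-Whitney U test in which patients who die in hospital, or who have not reached the event by discharge, are ranked last.
- **Alternative:** cumulative incidence compared with Gray's test. The event is solid food, bowel movement or discharge alive, and death is a competing event. Patients discharged without solid food must not be censored at discharge, because that would be informative. Keep them as not having reached the event up to a common time horizon.

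The two are not interchangeable if patients without the event are censored at discharge, so choose one and state it. How a withdrawal during the hospital stay is handled is a separate missing-data question.

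The cost is a few lines of text. Section 4.3 already takes bowel movement, solid food and days of hospitalization from the charts, and the first option needs nothing after discharge. Two downsides: the results are less familiar than a mean difference, and power is slightly lower if almost everyone reaches the event.

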6 REGULATORY ASPECTS AND SAFETY

During the entire duration of the study all serious adverse events (SAEs) where it cannot be excluded that the events are attributable to the intervention under investigation are collected, fully investigated and documented in source documents and case report forms (CRF). Study duration is defined from the time when the participant signs the informed consent until the last questionnaire after 3 months has been completed.

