3 STUDY OBJECTIVES AND DESIGN

3.1 Hypothesis and primary objective

The central hypothesis of the study is that intraoperative mechanical balloon dilatation of the pylorus performed by endoscopic balloon dilatation reduces the postoperative incidence of early DGCE.

There are various studies investigating the effectiveness of mechanical dilatation of the pylorus in reducing DGCE. In 2022, an RCT was published which investigated the efficacy of intraoperative balloon dilatation versus pyloroplasty versus no pylorus intervention. In this study, however, all patients underwent open surgery and none of the dilatations were performed endoscopically (19). In the era of minimally-invasive surgery we want to find a measure to reduce the incidence of DGCE during the postoperative course. This study would be, to our knowledge, the first RCT of its kind worldwide investigating intraoperative endoscopic balloon dilatation to prevent DGCE in patients with esophageal cancer undergoing minimally invasive surgery. We investigate the effectiveness of intraoperative balloon dilatation in reducing the incidence of postoperative DGCE in patients undergoing minimally invasive esophagectomy for esophageal cancer. In addition, we will detect potential complications associated with intraoperative balloon dilation of the pylorus as well as to prove that intraoperative balloon dilatation reduces DGCE associated complications, for example pneumonia. Furthermore, we want to analyze if the postoperative quality of life is improved in patients with intraoperative balloon dilatation. The findings of this study will make a substantial contribution to surgical practice and patient care in esophageal cancer.

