6.1 Local regulations / Declaration of Helsinki

This study is conducted in compliance with the protocol, the current version of the Declaration of Helsinki, the ICH-GCP, the HRA as well as other locally relevant legal and regulatory requirements.

6.2 (Serious) Adverse Events and notification of safety and protective measures

An **Adverse Event (AE)** is any untoward medical occurrence in a patient or a clinical investigation subject which does not necessarily have a causal relationship with the trial procedure. An AE can therefore be any unfavourable or unintended finding, symptom, or disease temporally associated with a trial procedure, whether or not related to it.

A **Serious Adverse Event (SAE)** (ClinO, Art. 63) is any untoward medical occurrence that results in death or is life-threatening, requires in-patient hospitalization or prolongation of existing hospitalization or results in persistent or significant disability or incapacity.

Both Investigator and Sponsor-Investigator make a causality assessment of the event to the trial intervention, (see table below based on the terms given in ICH E2A guidelines). Any event assessed as possibly, probably or definitely related is classified as related to the trial intervention.

Relationship	Description
Not related	- The event started in no temporal relationship to the project-specific intervention applied and

	
 - The event can be definitely explained by underlying diseases or other situations. - Causal relationship can be ruled out
Related	
 - The event started in plausible time relationship to the project-specific intervention applied and - The event cannot be definitely explained by underlying diseases or other situations.

Both Investigator and Sponsor-Investigator make a severity assessment of the event as mild, moderate or severe. Mild means the complication is tolerable, moderate means it interferes with daily activities and severe means it renders daily activities impossible.

Reporting of SAEs (see ClinO, Art. 63)

All SAEs are documented and reported immediately (**within a maximum of 24 hours**) to the Sponsor-Investigator of the study.

If it cannot be excluded that the SAE is attributable to the intervention under investigation, the Investigator reports it to the Ethics Committee via BASEC **within 15 days**.

Follow up of (Serious) Adverse Events

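### Sections 6 and 6.2 disagree on which SAEs are collected; if section 6 governs the CRF, SAE counts cannot be validly compared between the arms

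*Protocol*

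**What the plan says.** Section 6 sets the scope of SAE collection for the whole study, from consent to the last 3-month questionnaire: "all serious adverse events (SAEs) where it cannot be excluded that the events are attributable to the intervention under investigation are collected". It is also the sentence that sends SAEs to the source documents and the CRF.

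Section 6.2 sets a different scope for reporting to the Sponsor-Investigator: "All SAEs are documented and reported immediately", within 24 hours at most. It does not say where this documentation is kept. Attributability appears there as the trigger for the 15-day report: "If it cannot be excluded that the SAE is attributable to the intervention under investigation, the Investigator reports it to the Ethics Committee via BASEC".

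On causality, section 6.2 says "Both Investigator and Sponsor-Investigator make a causality assessment of the event to the trial intervention". The first criterion for a related event is "The event started in plausible time relationship to the project-specific intervention applied and", followed by the lack of a definite other explanation.

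Section 3.1 states a safety aim: "we will detect potential complications associated with intraoperative balloon dilation of the pylorus".

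**The concern.** In a randomised trial, a safety comparison rests on events being collected by the same rule in both arms, whatever anyone thinks caused them. Section 6 makes a causality judgement the condition for entering the SAE dataset. The control arm has neither a dilatation nor a sham (section 3.3), so that condition does not mean the same thing in the two arms.

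Section 6.2, read alone, has no such problem: everything is documented, and causality is judged afterwards for reporting. Staff who follow section 6 would leave SAEs judged unrelated out of the CRF, while staff who follow section 6.2 might enter them. The SAE dataset would then depend on which sentence was read. At stake are the aim in section 3.1 and the option in section 6.5 to stop early for evidence of harm. Both need SAE counts that can be set against a control.

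**Working it through.** **1. The two rules side by side**

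| | Section 6 | Section 6.2 |
|---|---|---|
| SAEs covered | Those whose attribution cannot be excluded | All |
| Where recorded | Source documents and CRF | Documented (place not stated), sent to the Sponsor-Investigator |
| Role of attributability | Condition for collection | Trigger for the 15-day Ethics Committee report |

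The first and third rows cannot both hold for one SAE dataset. Section 6.3 fits section 6.2 better: it asks for a yearly list of safety events with their causality, which says little if events were already filtered on causality.

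**2. Who applies the filter**

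The Investigator and the Sponsor-Investigator judge causality. Section 3.3 describes blinding for ward physicians and radiologists. It says that the operating surgeon knows the group and that unblinding is permitted when adverse events occur. It does not say whether the causality assessors are blinded, so there are two cases:

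- *Assessor knows the allocation.* Attribution to a dilatation that was not given can always be excluded. The section 6 set is then empty in control by construction.
- *Assessor is blinded.* Some control SAEs would stay in the set, and the expected imbalance disappears. SAEs judged unrelated are still lost from the CRF in both arms.

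**3. Illustration of size**

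The protocol states no SAE rate and no safety power, so there is no figure of its own to reproduce here. From section 5.1: 58 patients per arm. Assumptions not in the protocol: the same true SAE risk *p* in both arms, and attribution left open for a share *q* of dilatation-arm SAEs and for none in control.

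SAEs in the CRF under section 6, dilatation arm: k = 58 × p × q, rounded; control: 0. Spurious risk difference: k / 58. Two-sided Fisher's exact test of k/58 versus 0/58.

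| p | All SAEs per arm | q = 10% | q = 25% | q = 50% | q = 100% |
|---|---|---|---|---|---|
| 20% | 12 | 1 v 0 (p = 1.0) | 3 v 0 (0.24) | 6 v 0 (0.027) | 12 v 0 (0.0003) |
| 30% | 17 | 2 v 0 (0.50) | 4 v 0 (0.12) | 9 v 0 (0.003) | 17 v 0 (<0.0001) |
| 40% | 23 | 2 v 0 (0.50) | 6 v 0 (0.027) | 12 v 0 (0.0003) | 23 v 0 (<0.0001) |

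Worked cell: 58 × 0.30 × 0.50 = 8.7, so 9 versus 0, a difference of 9/58 = 15.5 percentage points. Over the whole grid the spurious difference runs from 1/58 = 1.7 to 23/58 = 39.7 points. Fisher's p falls below 0.05 from 6 versus 0 upward (5 versus 0 gives 0.057). With all SAEs recorded in both arms, the expected difference is 0 in every cell.

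In the blinded case with p = 30% and q = 25% in both arms, about 4 of 17 SAEs per arm reach the CRF and about 17 − 4 = 13 do not.

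**The case against.** The strongest reply is that section 6 is a loosely worded introduction and section 6.2 is the operative rule. Section 6 does not say in terms that other SAEs go unrecorded. Section 6.2 already requires all SAEs to be documented, and sections 8.1 and 8.2 say that all patient and study data are entered in REDCap. On that reading the protocol already does what is asked. This may well be the intention, but it does not remove the conflict. Section 6 is the only sentence that says which SAEs go into the CRF, and the general wording in section 8 does not say which SAEs count as study data.

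Second, a reader might infer that the trial has no valid safety comparison at all. The documents do not support that. Clavien-Dindo complication rates are a secondary endpoint (synopsis). Leak and pneumonia are compared between groups (section 3.2). Blinded ward physicians record complications (sections 3.3 and 4.3). Adverse events are scheduled for all patients on days 0, 5 and 10 and at 3 months (Appendix 1). None of these carries a causality filter. This objection stands and confines the point to the SAE dataset.

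Third, a reader might take the empty control arm as certain, or 17 versus 0 as the expected result. Neither follows. The first needs assessors who know the allocation. The second also needs an assumed 30% risk and every dilatation-arm SAE left open. The protocol plans no test of attribution-filtered SAE counts, so the p-values only gauge the size of the imbalance.

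Fourth, a reader might want the causality table in section 6.2 rewritten so that anything short of every not-related criterion counts as related. The text does not carry that. The not-related row has a third line, that a causal link can be ruled out, and how its lines combine is unclear. The sentence above the table also covers doubtful cases: "Any event assessed as possibly, probably or definitely related is classified as related to the trial intervention". Since the dilatation is done during the esophagectomy, such a rule would class nearly every early postoperative SAE in that arm as related and would widen the asymmetry.

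**Conclusion.** The contradiction is on the face of the protocol and needs no assumption. Section 6 makes attributability a condition for collection and CRF entry; section 6.2 makes it a condition for Ethics Committee reporting only. If section 6 governs the CRF, SAE counts cannot be validly compared between arms. That consequence rests on causality assessors who know the allocation, which the protocol neither states nor rules out.

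The imbalance cannot be sized from the documents. Under the assumptions shown it ranges from negligible (1 versus 0) to large (23 versus 0), depending mainly on how often attribution is left open. The sample size and the primary analysis are unaffected. The point should be corrected, but it does not undermine the trial's safety evidence as a whole.

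**What to change.** In section 6, delete the clause that restricts collection to possibly attributable events, and state that all SAEs in both arms, from consent to the 3-month questionnaire, are entered in the CRF regardless of causality. Leave section 6.2 as it is: causality is assessed after recording, and attributability remains the trigger for the 15-day Ethics Committee report. No change to the causality table is needed for this point.

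The cost is one sentence and some additional CRF entries. Section 6.2 already requires these events to be documented and sent to the Sponsor-Investigator within 24 hours, so the extra work is transcription. Sample size and power do not change.
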